6.10.2 Definition of DLT-Evaluable Patients for the Dose-Determining Set

Patients are considered as DLT-evaluable if they meet one of the following criteria:

- Experienced a DLT during the 28-day DLT evaluation period, **OR**
- Did not experience a DLT during the 28-day DLT evaluation period, received at least 3 of the 4 planned doses of IMCnyeso (including at least 2 doses at the target dose level), and were observed for \geq 28 days following the first dose

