1. Intra-patient escalation (IPE) regimens have been shown to improve tolerability of other CD3 bispecifics, including blinatumomab and the related ImmTAC molecule tebentafusp ([Saber, 2017](#)). Per Protocol Amendment 2, the Study Safety Team may initiate a 1-step or 2-step IPE regimen; a new higher dose level must be tested using a fixed-dose regimen before it is assessed in a 1-step IPE regimen and, similarly, a new higher dose level must be assessed using a 1-step IPE regimen before that dose can be assessed using a 2-step IPE regimen. However, it is anticipated that the risk to patients from acute mechanism-related toxicities is progressively reduced when moving from a fixed-dose regimen to a 1-step IPE regimen, and further reduced when moving from 1-step to a 2-step IPE regimen. Therefore, the dose-escalation rules have been updated, so that at any escalation step, a new permitted dose level based on the Bayesian Logistic Regression Model (BLRM) can be assessed using the same regimen as the prior cohort or using a regimen with additional steps. Furthermore, because ImmTAC-associated toxicities are generally acute, a 28-day DLT period will be used for all schedules.
2. Based on the observation that all signs/symptoms of cytokine release syndrome (CRS), to date, have occurred rapidly (within a few hours) following administration of IMCnyeso, once dose-escalation is completed and the Study Safety Team (SST) has reviewed all available relevant data for at least 6 patients at the recommended Phase II dose (RP2D), the SST may decide to reduce the minimum required post-end of infusion monitoring time to no less than 8 hours on Cycle 1 Day 1 (C1D1), C1D8, and/or C1D15 during the Phase II portion of the study. Such a decision will take into account the initial assessment of safety at the RP2D including whether treatment is well-tolerated at the selected RP2D and if any signs/symptoms of CRS occur within 2-4 hours post-end of infusion. Consistent with prior versions of the protocol, hospitalization would be extended if clinically indicated for any given patient.
3. Eligibility criteria were updated based on Investigator feedback as follows:

- a. Patients with a clinically stable, asymptomatic Grade 2 endocrine disorder due to prior anticancer therapy (previously restricted to hypothyroidism) are permitted to be enrolled in the study

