Study Design	
Phase I Dose Escalation:
 
Dosing will begin with the minimum anticipated biological effect level (MABEL) dose as determined by in vitro toxicology studies. Cohorts will initially enroll 3 to 6 patients. If necessary and deemed appropriate by the Study Safety Team (SST), additional patients may be enrolled in a given cohort to make informed dosing decisions. Cohorts of 2 patients may be considered for the first 2 doses. The initial dosing of patients in Phase I will be staggered, with at least a 1-week interval between the first 2 patients treated at each dose level.
 
Patients will be observed for dose-limiting toxicities (DLTs) for a period of 1 cycle (28 days). Dose-escalation or de-escalation decisions will be determined following review of all available safety, PK, and efficacy data, and the dosing recommendations will be primarily guided by the Bayesian Logistic Regression Model (BLRM). The key decisions of dose escalation or de-escalation and identification of the MTD and/or the RP2D will be made by the SST and will occur during the dose-escalation teleconferences (DETC), which will be held once all patients in a given dosing cohort have completed DLT evaluation. All dosing decisions will be agreed upon and documented in the DETC meeting minutes. The SST will include the Study Investigators, the Sponsor Medical Monitor, and a statistician.
 
If the emerging safety profile indicates that the severity of cytokine-mediated AEs tends to become less severe following repeated dosing, the SST may initiate a 1-step or 2-step intra-patient escalation (IPE) regimen and/or allow pre-medication as these approaches have been beneficial for related therapeutics.
 
Approximately 27 patients are predicted to be enrolled in Phase I.
 
Phase II Expansion:
 
Following the identification of the MTD and/or RP2D in Phase I, patients may be enrolled into the 3 Phase II expansion cohorts (NSCLC, urothelial carcinoma, and synovial sarcoma) to make a preliminary assessment of the anti-tumor activity of single-agent IMCnyeso at the RP2D in these disease settings.
 
A Simon two-stage design will be used for each Phase II cohort. If there are no responses among the first 9 patients in a cohort, then accrual in that cohort will stop. If there is at least one response, at the discretion of the Sponsor up to an additional 15 patients may be accrued for a total of up to 24 patients (with at least 3 responses to support further evaluation).

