6.2 Treatment Regimen and In-Patient Hospitalization

Patients enrolled in this study will receive treatment with single-agent IMCnyeso dosed weekly on Days 1, 8, 15, and 22 of each 4-week cycle. All dosages prescribed and dispensed to patients and all dose changes during the study must be recorded on the Dosage Administration Record and electronic case report form (eCRF).

For each administration of study medication, a physician must be present at the site or immediately available to respond to emergencies. Study sites will be instructed on the conservative management of symptoms associated with CRS (eg, hypotension), as described in [Section 6.15](#). Fully functional resuscitation equipment and medications to handle acute infusion-related emergencies (eg, anaphylaxis, CRS) must be available at each study site.

Patients will be hospitalized for 2 nights following the administration of the first dose (C1D1) of IMCnyeso and will remain at the site for overnight observation following administration of the second dose (C1D8). In addition, patients receiving intra-patient escalation (IPE) will be hospitalized overnight following the first three doses (C1D1, C1D8, and C1D15). After reviewing safety, PK, and cytokine data from at least 3 patients enrolled at a given dose level, the SST may decide that 1 night of hospitalization is adequate after the first dose for subsequent

patients (with longer hospitalization if indicated). After Phase I is completed and the SST has reviewed all available relevant data for at least 6 patients at the RP2D, the SST may decide to reduce the minimum required monitoring time during the Phase II portion of the study to no less than 8 hours post-end of infusion on C1D1, C1D8, and/or C1D15 (with longer hospitalization if clinically indicated). Patients who experience certain AEs may require additional in-patient monitoring as described in [Section 6.15](#).

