Figure 6-2: Schematic Illustration of a 2-Step IPE Regimen

Rules for the 2-step IPE regimen are as follows:

- The initial target dose level must be a permitted escalation step based on BLRM output and the consensus of the SST
- The initial target dose level must not exceed the 1-step dose-escalation MTD (if established)
- The C1D8 dose level must be at least one dose level below the initial target dose, and must be a dose level that has been evaluated in ≥ 3 patients using a fixed-dose or 1-step IPE regimen, with a decision to escalate based on the BLRM output and SST review of all available relevant data
- Escalation of the target dose in subsequent cohorts may proceed as in the main and 1-step dose escalation:
 - Separate MTD/RP2D may be identified using fixed-dose, 1-step IPE, and 2-step IPE regimens
 - DLT will be attributed to the dose level of the most recently administered dose prior to onset of the DLT (eg, a DLT with onset on C1D4 would be attributed to the C1D1 dose level, while a DLT with onset on C1D10 would be associated to the C1D8 dose level)
- The dose levels for C1D1 and C1D8 remain fixed for all subsequent cohorts
- Patients receiving 2-step IPE must receive the C1D1 and C1D8 doses prior to receiving the target dose
- If a 2-step IPE regimen is evaluated in Phase I, it may be selected for further evaluation in Phase II

An example of how IPE might be implemented is shown in [Figure 6-3](#).

[figure not shown]

Figure 6-3: Representative Escalation Path Incorporating IPE

IPE = intra-patient escalation.

Actual dose levels will be determined using BLRM and must be approved by SST. In this scenario, after 3 patients were enrolled in Cohort 4 and completed DLT evaluation, the recommended next dose per BLRM was 195 mcg. The SST determined that the 195 mcg dose would be better tolerated using a 2-step escalation regimen, and so Cohort 5 was opened with a dose of 30 mcg on C1D1, 100 mcg on C1D8, and 195 mcg as the target dose (weekly starting on C1D15).

In addition, a patient who is enrolled in a lower dose cohort may move to a higher dose cohort once all the following criteria are met:

- The patient has completed at least 3 cycles of treatment
- The patient did not experience any DLT or any \geq Grade 3 treatment-related toxicity
- The patient does not have any ongoing \geq Grade 2 treatment-related toxicity
- The higher dose cohort has completed SST review with a decision to escalate or was determined to be the MTD/RP2D

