7.2 Treatment Period Schedule

The treatment period starts with Day 1 of Cycle 1 (C1D1). A treatment cycle is defined as 28 days for the purposes of scheduling procedures and evaluations.

Any assessments required on C1D1 that are also performed as part of Screening do not need to be repeated on C1D1 if the data were obtained 72 hours prior to the first dose of study treatment. For subsequent visits, pregnancy testing may be performed up to 72 hours prior to dosing and other safety assessments may be performed up to 24 hours prior to dosing.

During the study visits, all tests and/or procedures should occur on schedule whenever possible. A visit window of ± 7 days (with a minimum of 7 days between doses of IMCnyeso) is allowed unless otherwise indicated in the protocol. If study drug infusions are delayed, the assessments associated with those infusions should be rescheduled accordingly. However, the timing of protocol-specified radiological assessments should be calculated in weeks using C1D1 as reference and should not be adjusted because of delays in treatment.

Assessments required during the treatment period are presented by visit in [Table 7-2](#). For patients receiving IPE, follow the alternate Cycle 1 schedule provided in [Section 13.4](#). Assessments marked “X” should be performed prior to dosing. Assessments that are to be performed at multiple timepoints are marked with the number of timepoints (including optional timepoints, if applicable) for the visit (eg, 2 \times is twice) and details of the timepoints are provided in the footnote. Additional details regarding the assessments are provided in [Section 7.4](#). Please refer to [Section 6](#) for dosing details. Patients will continue treatment until they meet criteria for discontinuation, as described in [Section 6.16](#).

Table 7-2: Schedule of Treatment Period Assessments

Procedure	Cycle 1						Cycle 2				Cycle 3				Later Cycles			
Day of Cycle	1	2	8	9	15	22	1	8	15	22	1	8	15	22	Visits on Days 1, 8, 15, and 22			
Adverse events	X	X	X	X	X	X	X	X	X	X	X	X	X	X		X		
Concomitant medications	X	X	X	X	X	X	X	X	X	X	X	X	X	X		X		
Safety Assessments																		
Complete physical examination	X																	
Abbreviated physical examination			X		X	X	X	X	X	X	X	X	X	X		D1 of each cycle		
Weight	X						X				X						D1 of each cycle	
Vital signs	~14x	~14x		3x	3x	3x	3x	3x	3x	3x	3x	3x	3x	3x		3x each dosing day		
12-lead ECG (single)	2x						2x				2x					2x on C4D1, C5D1, and C6D1		

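### The DLT-evaluability rule puts no date limit on the qualifying doses, so a 2-step IPE patient whose second target dose falls on Day 29 can count as DLT-free

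*Protocol*

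**What the plan says.** The Protocol Synopsis fixes the DLT window at one cycle: "Patients will be observed for dose-limiting toxicities (DLTs) for a period of 1 cycle (28 days"). The rationale for Global Amendment 3 confirms that "a 28-day DLT period will be used for all schedules", so IPE regimens get no longer window.

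Protocol Section 6.10.2 sets three conditions for a patient without a DLT:
- "Did not experience a DLT during the 28-day DLT evaluation period";
- the patient "received at least 3 of the 4 planned doses of IMCnyeso (including at least 2 doses at the target dose level");
- observation for at least "28 days following the first dose".

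Section 6.2 gives the nominal schedule, "dosed weekly on Days 1, 8, 15, and 22 of each 4-week cycle". Section 7.2 allows a visit window of 7 days either way, "with a minimum of 7 days between doses of IMCnyeso) is allowed unless otherwise indicated". It also says that when an infusion is delayed, its assessments move with it. Section 6.10.1 starts the 2-step target dose on C1D15 and adds: "Patients receiving 2-step IPE must receive the C1D1 and C1D8 doses prior to receiving the target dose".

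SAP Section 4.3.6 defines the dose-determining set by pointing to SAP Section 3.4, which refers back to Protocol Section 6.10.2. No dosing-date rule is added there. Sections 6.2, 6.10, 6.12 and 13.4 of the protocol contain no Cycle 1 or IPE exception to the visit window.

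**The concern.** The rule requires two target doses, presumably so that a patient counted as DLT-free has been observed on that dose twice. It counts doses and counts days from the first dose, but it does not link the two. A target dose given after the period has closed still satisfies the count, yet it adds no DLT information.

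The model in Section 13.3.1 treats each patient's outcome as yes or no, with no weight for partial follow-up. A patient with a late second target dose therefore counts the same as one dosed on schedule. This matters most in the 2-step cohorts. SAP Table 1 lists them as Cohort 6 (30-100-180 mcg, 4 enrolled) and Cohort 7 (30-100-300 mcg, 6 planned), which have the highest target doses in the table. Under Section 6.11 the MTD can rest on as few as 6 patients.

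**Working it through.** **Inputs.** DLT period Day 1 to Day 28 (Synopsis; Section 6.10.2). Nominal doses on Days 1, 8, 15 and 22 (Section 6.2). In 2-step IPE the target doses are the third and fourth (Section 6.10.1). Window of 7 days either way, with at least 7 days between doses (Section 7.2). I read the window as running from the nominal day counted from C1D1. A window rolling from the previous actual dose would allow longer slips.

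**Nominal check.** Four weekly doses × 7 days = 28 days, the plan's own period. Days of observation from a dose on Day d, counting the dosing day, are 28 − d + 1:
- first target dose, Day 15: 28 − 15 + 1 = 14;
- second target dose, Day 22: 28 − 22 + 1 = 7.

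**Doses needed.** Both lead-in doses are mandatory, so two target doses mean 2 + 2 = 4 doses. The 3-of-4 allowance gives no relief in 2-step IPE. That makes the rule stricter there and is not a fault in itself.

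**Effect of a slip.** If the schedule slips by k days before the first target dose, the target doses fall on Days 15 + k and 22 + k. They have 14 − k and 7 − k days inside the period.

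| Slip k (days) | Target doses on Days | Days observed, first | Days observed, second |
|---|---|---|---|
| 0 | 15, 22 | 14 | 7 |
| 1 | 16, 23 | 13 | 6 |
| 3 | 18, 25 | 11 | 4 |
| 6 | 21, 28 | 8 | 1 |
| 7 | 22, 29 | 7 | 0 |

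**Does the k = 7 patient meet the rule?** Take Days 1/15/22/29 or 1/8/22/29. Each dose is within 7 days of its nominal day, and each gap is at least 7 days. All four planned doses are given, two at target. Day 29 is 28 days after Day 1. Every condition in Section 6.10.2 is met on the day of the second target dose itself. If the slip arises between the two target doses (Days 1/8/15/29), the first keeps its 14 days and the second still has none.

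Of the 120 whole-day schedules that the window and the 7-day gap allow, 36 put the fourth dose on Day 29. This counts schedules and is not a probability.

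**1-step IPE.** With the same slip and all doses given (Days 1/15/22/29), target doses on Days 15 and 22 are still inside the period. The problem arises only if one dose is omitted under the 3-of-4 allowance and the last is given on Day 29, for example Days 1/15/29.

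**Illustration, under assumptions.** Let the true DLT risk over two target doses be 0.33, and let the second-dose risk be r times the first-dose risk q. Solve 1 − (1 − q)(1 − rq) = 0.33:
- r = 0.25 gives q = 0.28;
- r = 1 gives q = 0.18.

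If only the first target dose is seen in all three patients of a cohort, P(no DLT in 3) rises from 0.67³ = 0.30 to between 0.37 (r = 0.25) and 0.55 (r = 1). If one patient of the three is affected, it is 0.67² × (1 − q), or 0.32 to 0.37. The documents give neither r nor the frequency of slips, so these figures show scale only.

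**The case against.** The strongest reply is that the rule already means doses given in the period. There are four planned doses only because the period is one cycle, and Day 29 is nominally C2D1. On that reading the Day 29 patient has three doses and one at target, is not evaluable, and may be replaced. This is a sensible intention, but the text does not state it, and a C1D22 dose on Day 29 is within the window that Section 7.2 allows.

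The second reply is Section 6.12. The Study Safety Team may count a later event as a DLT, and under Section 6.10 it reviews all relevant data. This is a real mitigation, but it is optional. The escalation meeting takes place once the cohort has completed DLT evaluation, which this patient does on Day 29. The separate provision for toxicity-related delays in Cycle 1 needs more than 7 days, so a 7-day slip escapes it.

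The third reply concerns the size of the effect, and much of it stands. The protocol reports that signs of cytokine release have so far appeared within a few hours of dosing, and IPE is used when such events lessen on repeat dosing. The first target dose, plausibly the riskier, still has 7 days. This covers cytokine-mediated events better than the rest of Table 6-3, which also has criteria based on persistence, such as Grade 3 liver abnormalities unresolved at 14 days.

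A reader might infer that escalation is biased upward because delays follow toxicity. The documents do not support this. Table 6-4 requires a dose reduction after Grade 3 CRS, after Grade 3 rash that takes 7 to 21 days to resolve, and after isolated Grade 3 liver abnormalities in the lower range that take more than 7 days. A patient reduced before a second target dose does not meet the two-at-target condition. What remains is mainly administrative or lower-grade delay, and nothing shows that a Cohort 6 or 7 patient was delayed.

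**Conclusion.** The gap is real and is essentially confined to 2-step IPE. As written, Sections 6.10.2 and 7.2 together admit a non-DLT patient whose second target dose had 0 days of observation instead of 7 and, if the slip came before the first target dose, whose first had 7 instead of 14. Slips of 1 to 6 days keep the second dose inside the period with 6 to 1 days after it. The day counts are exact for a Day 1 to Day 28 period and a window anchored to C1D1. If the period is read as 28 elapsed days, Day 29 is its closing boundary and the second dose still has essentially no observation.

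Any missed event can only lower the DLT rate observed at the target dose. The size is unknown. Halving the observation days (14 to 7 for the first target dose) might be read as losing half the DLTs, but days lost are not events lost when toxicity is mostly acute. Nor does an on-schedule patient have 14 days after both target doses: the second has 7. A 1-step schedule of Days 1/15/29 might be taken as two permitted delays, but a third planned dose on Day 29 would be 14 days late and out of window. It needs an omitted dose as well.

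**What to change.** Reconcile the two sections with one sentence in Section 6.10.2: for a patient without a DLT, the qualifying doses, including the two at the target level, must have been given within the 28-day DLT evaluation period. Otherwise the patient is not DLT-evaluable and may be replaced under Section 6.17. The same sentence should name the last day of the period, so that a Day 29 dose is classified the same way every time. The SAP definition follows by reference.

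This leaves the 28-day period unchanged. Extending the period for individual delayed patients would reopen a choice that Amendment 3 made deliberately, with a stated rationale, for all regimens. Whether also to set a minimum observation time after the second target dose, which would address slips of 1 to 6 days, is for the sponsor to decide.

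The cost is an occasional replacement. On-schedule patients are unaffected, and so is a 1-step patient dosed on Days 1/15/22/29, who has three doses, two at target, by Day 22. A patient on any regimen who omits one dose and receives another on Day 29 would no longer be evaluable as a non-DLT.

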6.11 Definition of Maximum Tolerated Dose and Recommended Phase II Dose

The MTD will be determined if the following conditions are met:

1. At least 6 patients have been treated at this dose and associated treatment regimen (ie, fixed-dose, 1-step IPE, or 2-step IPE).
2. The dose has the highest posterior probability that the true DLT rate is in the target interval for toxicity (16%–33%), as predicted by the BLRM. The interval boundaries of 16% and 33% are chosen to be consistent with the traditional 3+3 design toxicity boundary (ie, 1/6 and 1/3).
3. The dose satisfies the EWOC principle (the probability that the DLT rate lies within the excessive toxicity or the unacceptable toxicity window is less than 25%).

The RP2D will be defined as the dose and associated treatment regimen selected for further evaluation in Phase II by the SST. The RP2D will be determined from a synthesis of all data available, including safety, tolerability, PK, pharmacodynamics, and preliminary anti-tumor activity observations from Phase I. The RP2D must not exceed the MTD as determined by the BLRM. A minimum of 6 patients will be treated at the RP2D in Phase I and monitored through the DLT evaluation period before enrollment in Phase II may begin.

During Phase II, following enrollment of at least 12 subjects, if the observed rate of Grade 3 and/or Grade 4 toxicity considered related to IMCnyeso and meeting the definition of DLT is > 30%, a safety teleconference will be convened with the SST to determine if the cohorts should continue enrollment.

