3.2 Phase II Dose Expansion

Following the identification of the MTD and/or RP2D in Phase I, patients may be enrolled into the 3 Phase II expansion cohorts (NSCLC, urothelial carcinoma, and synovial sarcoma) to make a preliminary assessment of the anti-tumor activity of IMCnyeso as a single agent in these disease settings. Initially, up to 9 patients may be enrolled in each Phase II cohort. If there is at least one response, at the discretion of the Sponsor up to an additional 15 patients may be accrued for a total of up to 24 patients, as discussed in [Section 9.9.2](#).

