Table 6-2: Example IMCnyeso Dose Levels for Phase I Dose Escalation

Dose Level	Estimated IMCnyeso Dose Level	Planned Enrollment
1 (starting dose)	3 mcg	2–6
2	10 mcg	2–6
3	30 mcg	3–6
4	100 mcg	3–6
5	190 mcg	3–6

To better understand the safety, tolerability, and PK profile of single-agent IMCnyeso, additional cohorts of patients may be enrolled at preceding dose levels or intermediate dose levels, before or in parallel, while proceeding with further dose escalation. The outcome from these cohorts will be included in the BLRM.

If the first 2 patients in a previously untested dose level experience a DLT, additional enrollment in that cohort will stop, the BLRM will be updated with this new information, and the SST will evaluate the available safety, PK, and pharmacodynamic data. By incorporating information gained at the preceding dose levels and provided the BLRM predicts that the risk of excessive toxicity remains below 25% (EWOC), additional patients may be enrolled at this dose level or a lower dose level as agreed upon by the SST.

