9.9.2 Phase II Expansion Cohorts

A Simon two-stage design will be used for each Phase II cohort using a 10% probability of a Type 1 error, a 20% probability of a Type 2 error, and assuming a target response rate of 20% versus 5% response rate for available treatment options. If there are no responses among the first 9 patients in a cohort, then accrual in that cohort will stop. If there is at least one response, at the discretion of the Sponsor up to an additional 15 patients may be accrued for a total of up to 24 patients (with at least 3 responses to support further evaluation).

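### In Phase II no SST safety call is mandatory before the 12th subject, although four affected subjects already settle that the 30% trigger will be crossed at 12

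*Protocol*

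**What the plan says.** The Phase II trigger is in the last paragraph of Protocol Section 6.11. It opens, for Phase II, with "following enrollment of at least 12 subjects, if the observed rate of Grade 3 and/or Grade 4 toxicity", limits the events to those "considered related to IMCnyeso and meeting the definition of DLT is > 30" per cent, and gives the consequence: "a safety teleconference will be convened with the SST to determine if the cohorts should continue enrollment". The section does not say whether the rate is per subject or per event, or whether the 12 subjects are counted over all cohorts or within one.

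Section 3.2 gives the accrual frame: "patients may be enrolled into the 3 Phase II expansion cohorts (NSCLC, urothelial carcinoma, and synovial sarcoma"), and "Initially, up to 9 patients may be enrolled in each Phase II cohort".

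The other safeguards do not require an SST meeting on the Phase II DLT rate:
- **Early-event rule, Section 6.10:** "If the first 2 patients in a previously untested dose level experience a DLT, additional enrollment in that cohort will stop". It applies to a dose level not tested before; the RP2D has been.
- **Staggered dosing, Section 6.4:** dose-escalation cohorts only.
- **Phase II interim analysis, Protocol Section 9.8 and SAP Section 11:** response only, at 9 patients per cohort.
- **24-hour notice, Section 8.5:** each DLT is reported to the Sponsor, with no SST meeting attached.
- **Stopping rules mentioned in Section 2.2:** these point to Section 6.15, which covers management of the individual patient.
- **SAP Section 8.1:** DLTs are to be summarised for Phase II where appropriate, with no mention of the trigger.

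**The concern.** A minimum sample size before a rate is read makes sense while the result could still go either way. Here it can be settled earlier. Once a fourth subject is affected, no later outcome can bring the rate at the 12th subject down to 30% or below. Waiting adds nothing to the decision to hold the call, while further subjects may be treated at the same dose before the SST is obliged to discuss continuing enrolment.

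Phase II may open with as few as 6 patients monitored through the DLT period at the RP2D. The overdose criterion tolerates a posterior probability of just under 25% that the true DLT rate is 33% or more (Sections 6.11 and 13.3.1). Section 6.2 also lets the SST shorten the minimum monitoring time after the Cycle 1 infusions during Phase II. A rate high enough to trip the trigger is therefore possible, though not the expected case.

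**Working it through.** **Figures the plan derives.** Section 6.11 gives no derivation or operating characteristics for the trigger, so there is nothing to reproduce for it. The derived Phase II figure is the Simon design in Section 9.9.2, set up "using a 10% probability of a Type 1 error, a 20% probability of a Type 2 error, and assuming a target response rate of 20" per cent against 5%. An exact two-stage binomial calculation (stop at 0 of 9; at least 3 of 24 needed) gives a Type 1 error of 0.0931 and power of 0.8047, so the design meets its limits. It concerns response and does not bear on the safety trigger.

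**Inputs from Section 6.11.** Minimum enrolment 12; threshold strictly above 30%; consequence a teleconference. Assumptions: counting is per subject and pooled over cohorts, and each outcome is known before the next enrolment. True rates of 16% and 33% are the protocol's target-interval limits; 30%, 40% and 50% are illustrative.

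**Step 1: smallest count that crosses at 12.** 3/12 = 25.0% does not exceed 30%; 4/12 = 33.3% does. The minimum is 4.

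**Step 2: certainty.** With 4 affected subjects by the 12th enrolment, the rate at 12 is at least 4/12 = 33.3%. It would still cross at 13 (4/13 = 30.8%) but not at 14 (4/14 = 28.6%).

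**Step 3: when the fourth affected subject appears.** Let N be that subject's number in order of enrolment and p the true rate. Then

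P(N = k) = C(k−1, 3) · p⁴ · (1−p)^(k−4), for k = 4, …, 12.

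P(crossing at 12) = sum of P(N = k) over k = 4 to 12, which equals P(at least 4 of 12).

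The number enrolled after the fourth affected subject and up to the 12th is 12 − N. Its unconditional mean U is the sum of (12 − k) · P(N = k); its mean given crossing is U / P(crossing).

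Check at p = 0.40: P(0, 1, 2 or 3 of 12) = 0.0022 + 0.0174 + 0.0639 + 0.1419 = 0.2254, so P(crossing) = 0.775 after rounding. U = 2.826, and 2.826 / 0.7747 = 3.65 (3.649 unrounded).

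| True rate (assumed) | P(at least 4 of 12) | Mean enrolled after 4th affected, given crossing | Unconditional mean | P(first 4 all affected) = p⁴ |
|---|---|---|---|---|
| 16% | 0.11 | 2.2 | 0.2 | 0.1% |
| 30% | 0.51 | 2.9 | 1.5 | 0.8% |
| 33% | 0.60 | 3.1 | 1.9 | 1.2% |
| 40% | 0.77 | 3.6 | 2.8 | 2.6% |
| 50% | 0.93 | 4.5 | 4.2 | 6.3% |

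**Step 4: the extreme.** The maximum is 12 − 4 = 8 further subjects. It requires all of the first four to be affected, which is the last column.

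**The case against.** The strongest reply is that little is lost. The rule leads to a teleconference, not a halt. The Sponsor hears of every DLT within 24 hours, may end the study at any time (Section 3.7), and nothing bars an earlier SST meeting. The RP2D may not exceed an MTD that satisfies the overdose criterion, so rates of 40% to 50% are not the central case. Within the target interval the unconditional expectation is only 0.2 to 1.9 subjects. All of this stands. It limits the point to a mandatory early call, but does not remove it: a written trigger exists so that review does not depend on discretion.

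Three stronger readings are tempting, and the documents do not support them.
- **Eight more subjects as the typical exposure.** Eight is the arithmetical maximum, with probability 6.3% or less at rates up to 50%.
- **The rule dilutes the rate with newly enrolled, unobserved subjects.** Section 6.11 makes enrolment of 12 the starting condition and then speaks of an observed rate. It does not say that the denominator is everyone enrolled. At least 12 is also a minimum rather than a single look, so the rate can be read again as follow-up matures.
- **The rule is silent throughout stage 1 because each cohort pauses at 9.** That follows only if the 12 are counted within a cohort. The reference to Phase II and to the cohorts in the plural favours pooling, though the text does not settle it.

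Nor does the Phase I early-event rule set a standard that Phase II breaks, since it is confined to untested dose levels.

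**Conclusion.** The point holds as a gap in a mandatory review, not as an error or contradiction in the protocol. With pooled, per-subject counting, four affected subjects settle the outcome at 12, and no provision requires the SST to meet before then. When the trigger is crossed, the delay averages roughly two to five subjects across assumed true rates of 16% to 50%; averaged over all outcomes it is 0.2 to 4.2.

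These figures overstate what an early call could save, because they take each outcome as known before the next enrolment. With a 28-day DLT period, some later subjects would already be enrolled when the fourth event came to light. The certainty applies if the rate is read at 12 or 13 subjects. The change is worth making because it is cheap and concerns subject safety; the size does not support stronger language.

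**What to change.** Add to Protocol Section 6.11 that, before the 12th Phase II subject is enrolled, the SST teleconference is convened as soon as four different Phase II subjects, pooled over cohorts, have had a qualifying event. From 12 subjects onward the existing rule of more than 30% applies unchanged. State in the same place that the rate is per subject and pooled over cohorts. The threshold, the definition of a qualifying event and the consequence stay as they are.

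Confining the new clause to the period before the 12th enrolment matters: without that limit it would also call a meeting at 4/14 = 28.6%, below the protocol's own threshold.

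The cost is a short addition to the text, with no added patients or procedures. The change is not wholly neutral. It can produce a call that would not otherwise have occurred, if Phase II enrolment never reaches 12 (for example, if a single cohort opens and stops at 9) or if the rate is first read at 14 or more subjects.
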